8.3.2 Secondary Endpoints

Secondary efficacy endpoints are:

- Changes from baseline in the WOMAC total score and in the WOMAC pain, function, and stiffness index scores over 2 years
- Change from baseline in the 20-meter walk test over 2 years

- Change from baseline in the PGA over 2 years
- Change from baseline in minimal JSW in the medial and lateral compartments as evaluated by X-ray over 2 years
- Change from baseline in cartilage thickness in the medial and lateral compartments as well as in the total femorotibial joint over 2 years
- Change from baseline in cartilage volume in the medial and lateral compartments as well as in the total femorotibial joint over 2 years
- Synovial fluid levels of sprifermin/FGF-18
- Serum levels of sprifermin/FGF-18

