8.5.3 Analysis of Secondary Endpoints

Descriptive statistics for secondary efficacy endpoints will be presented by time point (visit) and treatment group.

The same ANOVA model used for the primary endpoint will be used to assess the treatment effect on continuous secondary endpoints such as MRI endpoints, WOMAC endpoints (total, pain, function, and stiffness scores), and X-ray endpoints at each time point and over time.

Logistic regression will be used to assess the treatment effect on the binary efficacy endpoints such as the OMERACT-OARSI responder rate. Point estimates for each pairwise comparison and corresponding 95% CIs and p-values will be provided.

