Trial Endpoints

Primary

Change from baseline in cartilage thickness in the total femorotibial joint as evaluated by MRI at 2 years

Secondary

- Changes from baseline in the Western Ontario and McMaster Universities Osteoarthritis Index (WOMAC) total score and in the WOMAC pain, function, and stiffness index scores over 2 years
- Change from baseline in the 20-meter walk test over 2 years
- Change from baseline in the Patient's Global Assessment (PGA) over 2 years
- Change from baseline in minimal Joint Space Width (JSW) in the medial and lateral compartments as evaluated by X-ray over 2 years
- Change from baseline in cartilage thickness in the medial and lateral compartments over 2 years
- Change from baseline in cartilage volume in the medial and lateral compartments over 2 years
- Synovial fluid levels of sprifermin/FGF-18
- Serum levels of sprifermin/FGF-18

Safety endpoints

- Nature, incidence and severity of local and systemic Adverse Events (AEs).
- Incidence of acute inflammatory reactions (AIRs), defined as increase of pain by 30 mm on a 100 mm visual analogue scale (VAS) and a self-

- reported synovial fluid effusion (i.e., joint swelling) within 3 days following i.a. injection (see Section 7.4.1.1 of the protocol)
- Changes in laboratory safety parameters, vital signs, 12-lead electrocardiogram (ECG) parameters, weight, and physical examinations
- Occurrence of binding and neutralizing antibodies to sprifermin/FGF-18

Exploratory

- Outcome Measures in Rheumatology Osteoarthritis Research Society International (OMERACT-OARSI) responder rate at 2 years
- Patient Global Impression of Change (PGIC) over 2 years
- Changes from baseline in the scores of the Knee Injury and Osteoarthritis
 Outcome Score quality of life subscale (KOOS QOL) and the SF-36
 Medical Outcomes Study Short Form-36 General Health Survey (MOS
 SF-36 questionnaire) over 2 years
- Change from baseline in Knee Injury and Osteoarthritis Outcome Score (KOOS) Symptom Index over 2 years
- Change from baseline in Numerical Rating Scale (NRS) pain score in the target and contralateral knee over 2 years using an 11-point NRS
- Change from baseline in presence of pain in other joints over 2 years
- Change from baseline in Measure of Intermittent and Constant Osteoarthritis Pain (ICOAP) scores over 2 years
- Change over time in structural features of the knee joint (e.g., synovium, menisci, bone, and other structures) as evaluated by MRI

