8.4 Interim analysis

No interim analysis prior to Year-2 analysis is planned.

9 Changes to the Planned Analyses in the Clinical Trial Protocol

The following clarifications and changes (including deletion and additional analyses) compared to the protocol have been made prior to database lock and breaking the blind of the study:

Deletion:

Interleukin-6 (IL-6) is not measured (see Note to File "Selection of Biomarkers for Clinical Study EMR700692-006") and therefore was removed from the list of laboratory parameters (Section 7.4.3 of the protocol).

Clarifications:

- 1. The protocol is not specific on what deviations are considered major and resulting in subjects who are excluded from the PP Analysis (Section 8.4 of the protocol). Section 10 provides more details for definition of major protocol deviations and the process to identify them.
- 2. The protocol is not specific on how data will be included in the extended follow-up period analysis (Section 8.5.1 of the protocol). Section 8.2 provides more details on what data will be included in this analysis. It also specifies that all data from the 5 years period will be included in this integrated analysis.
- 3. Clarification on time points, scored regions, scoring system and analyses for Whole Organ Magnetic Resonance Imaging Score (WORMS) and (Boston-Leeds Osteoarthritis Knee Score) BLOKS are provided in Section 16.5 (Section 8.5.5 of the protocol).

Additions:

- 1. Analysis sets. The following additional analysis set is specified in Section 10. For the long term follow-up phase (following day 819), a separate analysis set is defined consisting of subjects from the ITT population who have at least one post-treatment quantitative MRI assessment or at least one WOMAC measurement in the follow-up period, i.e., the Second ITT (ITT2). The ITT2 Analysis Set will include all subjects from the ITT Analysis Set who have at least one MRI assessment available or one X-ray assessment available or one WOMAC measurement on or after day 820.
- 2. Year-3 Analysis: A Year-3 Analysis is planned and described in Section 8.
- 3. Sensitivity analysis using LOCF. The LOCF method as imputation for missing data on post baseline observations will be used as sensitivity evaluation with potential to be utilized in future studies. This is described in Section 11.

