The WOMAC total score, and absolute changes from baseline in the WOMAC total score for the target knee will be presented with summary statistics for all timepoints (including baseline, post-treatment, and LOCF).

Absolute change from baseline in WOMAC total score over 2 years will be considered a continuous variable and will be analysed using a model similar to the ANOVA model used for the primary endpoint.

If an entire questionnaire is missing for a time point, no imputations will be performed for that time point. If some items are missing, imputation for Total score (and for sub scores) will be performed using same principal used for KOOS.

WOMAC Sub Scores

WOMAC sub scores (weight-bearing pain score (sum of items: walking, going up and down stairs, and standing), pain, function and stiffness) will be tabulated descriptively as described above for Total score.

Absolute change from baseline in pain, function, stiffness, and weight-bearing pain, over 2 years will be analysed using a model similar to the ANOVA model described under primary endpoint.

WALK test

Time needed to complete the 20-meter walk tests as well as absolute change from baseline will be presented with summary statistics per timepoint (including LOCF). No imputation for missing data will be done. Absolute change from baseline in time needed to complete the 20-meter walk will be analysed using a model similar to the ANOVA model described under primary endpoint.

Patient Global Assessment (PGA)

The Patient Global Assessment is based on subject's answer to the question "Considering all the ways your osteoarthritis of the knee has affected you during the last 48 Hours, select the number that best describes the impact of your knee osteoarthritis on your daily life", and can take on values between 0-10 (0=None, 10=Extreme), for summaries the values are rescaled to 0-100 by multiplication with 10.

The Patient Global Assessment will be presented with summary statistics per timepoint (including LOCF) as well as absolute change from baseline. Mean score will be presented as described for continuous variables, and also number and percentages per score will be presented. No imputation for missing data will be done (except LOCF).

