19.1 List of endpoints

Group	Endpoint	Treatment Phase	Follow-up (integrated)	Reference
		Baseline to LOCF1	Baseline to LOCF2	
Trial Subjects	Disposition	Descriptive	Descriptive	12
	Protocol Deviations	Descriptive	Descriptive	12.1
Demographics and other baseline characteristics	Demographics	Descriptive	Descriptive	13.1
	Medical History	Descriptive	Descriptive	13.2
	Baseline Characteristics	Descriptive	Descriptive	13.3
Concomitant Medication and procedures	Previous medication and procedures	Descriptive	Descriptive	14
	Concomitant medication and procedures	Descriptive	Descriptive	14
	Pain medication	Descriptive	Descriptive	14
Exposure and treatment compliance	Exposure	Descriptive	Descriptive	15
	Compliance	Descriptive	Descriptive	15
Efficacy	Change from baseline in average cartilage thickness in the total femorotibial joint as evaluated by MRI in the target knee	Primary: Descriptive Analysis Sensitivity analysis (PP) Model check	Exploratory: Descriptive Analysis Model check	16.1
	WOMAC total score in the target knee at baseline and post- baseline	Secondary endpoint Descriptive Analysis Sensitivity analysis (PP) Subgroup analysis	Exploratory: Descriptive Analysis Model check	16.2
	WOMAC sub scores in the target knee at baseline and post- baseline	Secondary endpoint Descriptive Analysis Sensitivity analysis (PP) Subgroup analysis	Exploratory: Descriptive Analysis Model check	16.2

Group	Endpoint	Treatment Phase	Follow-up (integrated)	Reference
		Baseline to LOCF1	Baseline to LOCF2	
	20-meter WALK test	Secondary endpoint Descriptive Analysis	Descriptive	16.2
	PGA	Secondary endpoint Descriptive	Descriptive	16.2
	JSW on X-ray in the target knee at screening or baseline – and post-treatment	Secondary endpoint Descriptive Analysis Sensitivity analysis (PP) Subgroup analysis	Exploratory: Descriptive Analysis Model check	16.2
	Regional Average Cartilage thickness on MRI	Secondary endpoints Descriptive Analysis	Descriptive	16.2
	Total and Regional Cartilage Volume	Secondary endpoint Descriptive Analysis	Descriptive	16.2
PK	Synovial fluid levels of sprifermin/FGF-18	Descriptive	NA	16.3
	Serum levels of sprifermin/FGF-18	Descriptive	NA	16.3
PK/Safety	Occurrence of antibodies	Descriptive	NA	16.3 and 17
Other endpoints	OMERACT-OARSI score for the target knee	Descriptive Analysis	Descriptive	16.5
	PGIC	Descriptive	Descriptive	16.5
	KOOS Qol Score	Descriptive	Descriptive	16.5
	KOOS Symptom index	Descriptive	Descriptive	16.5
	MOS SF-36 Score	Descriptive	Descriptive	16.5

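### PGA is the only secondary efficacy endpoint that the SAP leaves without the repeated-measures model, so no between-group estimate of change in PGA is prespecified, and Section 9 does not say so

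*SAP*

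**What the plan says.** Protocol 8.3.2 lists "Change from baseline in the PGA over 2 years" among the secondary efficacy endpoints. SAP Section 6 repeats it as secondary: "Change from baseline in the Patient's Global Assessment (PGA) over 2 years".

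On analysis, protocol 8.5.3 states: "The same ANOVA model used for the primary endpoint will be used to assess the treatment effect on continuous secondary endpoints". It then gives MRI, WOMAC and X-ray endpoints as examples, and the synopsis says the same.

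SAP 16.2 takes the 0-10 PGA answer, multiplies it by 10 for summaries, and then says: "The Patient Global Assessment will be presented with summary statistics per timepoint (including LOCF) as well as absolute change from baseline". It adds: "Mean score will be presented as described for continuous variables, and also number and percentages per score will be presented". No model, contrast or comparison with placebo follows. In the SAP 19.1 list of endpoints, the treatment-phase entry for PGA is "Secondary endpoint Descriptive" and stops there. The entries for the other secondary efficacy endpoints go on to include analysis.

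SAP Section 9 opens with "The following clarifications and changes (including deletion and additional analyses) compared to the protocol have been made prior to database lock". The only deletion listed there is interleukin-6. PGA is not mentioned under deletions, clarifications or additions.

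**The concern.** A secondary efficacy endpoint that the protocol appears to place under the mixed model becomes descriptive in the SAP, with no reason given and no entry in the list of changes.

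Evaluating symptoms is a secondary objective. Protocol Section 3 reports that in the proof-of-concept trial symptoms improved most on placebo, and says that this needs further investigation. SAP Section 11 adjusts only with Dunnett within models, and rests interpretation on all efficacy results together and on their consistency across endpoints. PGA can join that reading on equal terms only if it has an estimate and interval comparable with those for WOMAC and the walk test.

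By-visit means and LOCF summaries are not adjusted for baseline PGA or for pooled country. They also make less use of the repeated measurements than the model does, which matters more as dropout grows.

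**Working it through.** The documents give no effect size, SD or power for PGA, so there is no figure to reproduce. The check sets the passages side by side.

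**1. Which secondary efficacy endpoints get the model in the treatment phase?**

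| Endpoint | Among the examples in protocol 8.5.3 | Model in the SAP | SAP 19.1, treatment phase |
|---|---|---|---|
| WOMAC total and sub scores | yes | yes (16.2) | descriptive and analysis |
| Minimal JSW, medial and lateral | yes (X-ray) | yes (16.2) | descriptive and analysis |
| Cartilage thickness, medial and lateral | yes (MRI) | yes (16.2) | descriptive and analysis |
| Cartilage thickness, total | yes (MRI) | yes (16.1, as primary) | descriptive and analysis |
| Cartilage volume | yes (MRI) | yes (16.2) | descriptive and analysis |
| 20-meter walk test | no | yes (16.2) | descriptive and analysis |
| PGA | no | no | descriptive only |

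Protocol 8.3.2 also lists serum and synovial fluid drug levels, but these are pharmacokinetic measures handled in SAP 16.3. With those set aside, PGA is the only one without a model.

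**2. Does protocol 8.5.3 cover PGA?** Its examples are introduced as examples and do not name PGA. Two features of the SAP indicate that PGA belongs under the rule:
- The walk test is not named either, and the SAP still models it: "Absolute change from baseline in time needed to complete the 20-meter walk will be analysed using a model similar to the ANOVA model". The SAP therefore does not treat the examples as a closed list.
- The SAP puts PGA on a 0-100 scale and summarises its mean as for continuous variables.

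**3. Does another part of the SAP supply a between-group estimate of change in PGA?**
- The summary statistics in SAP Section 11 are computed within group.
- Section 11 also has a general convention for differences between groups, using unequal variances. Neither 16.2 nor 19.1 calls for such a difference for PGA, and it would not be baseline-adjusted.
- SAP 16.5 fits logistic regression to OMERACT-OARSI response. PGA is one of three domains there, enters only the moderate-improvement criterion, and is dichotomised. The regression runs only if more than 10% of the ITT set meets a criterion. It estimates an effect on an exploratory composite, not on change in PGA.

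**4. How much is left out?** Protocol Appendix E schedules PGA with WOMAC at Weeks 12, 26, 38, 52, 64, 78, 90 and 104, which is 8 post-baseline visits. The model code in SAP Section 11 gives each active arm against placebo and a linear trend at each visit. For PGA that would be 4 × 8 = 32 pairwise differences and 8 trend contrasts, plus the overall ones. None is planned.

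**5. What does dropout add?** Protocol 8.1 plans for about 30% discontinuation at two years: 109 × 0.70 = 76.3, the plan's 76 evaluable per group, which leaves 109 − 76 = 33 without Week 104 data. If dropout came near that rate, the raw Week 104 mean would ignore the earlier PGA values of those 33, and LOCF would carry their last value forward. The mixed model would use their earlier visits.

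**The case against.** The best case on the other side has four parts.

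**The protocol conflict is an inference.** PGA is a single 11-box item that protocol 8.5.3 does not name. SAP 16.2 says outright that WOMAC total is treated as continuous, makes no such statement for PGA, and adds counts per score. This stands as a qualification: the conflict depends on classing PGA as continuous. The handling of the PGA mean and of the walk test makes that the more natural reading.

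**The choice looks deliberate.** SAP 16.2 and 19.1 agree with each other, and Section 11 says only that several endpoints are modelled. That may be so, but a deliberate departure is what Section 9 exists to record.

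**PGA is still reported.** A reader might infer that the trial will show nothing about treatment and PGA. The documents do not support that: group means and changes by visit will appear, and PGA contributes to the OMERACT-OARSI response. What is missing is a prespecified between-group estimate, interval or test.

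**The dropout argument is easily overstated.** A reader might infer that 30% of PGA values will be missing at Week 104 and that the raw means compare different survivors by arm. The 30% is a planning rate for discontinuation, not observed PGA missingness, and nothing in the documents points to dropout differing by arm. Protocol 7.1.5 also asks for the Week 104 assessments at early discontinuation. SAP Table 3 assigns results to visits by study day, so an early assessment reaches Week 104 only through LOCF. It still gives some leavers a last value.

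It is also fair that PGA is absent from the power calculations and that WOMAC total, pain, function and stiffness are all modelled. Inference on symptoms does not rest on PGA.

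**Conclusion.** The point holds in a limited form. PGA is the only secondary efficacy endpoint for which the SAP plans no repeated-measures model, and Section 9 does not declare this. No estimate, confidence interval or test against placebo for change in PGA is prespecified for any of the four active arms.

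The finding of a departure from the protocol assumes that PGA counts as a continuous endpoint, as its handling in the SAP implies. The absence of an estimate does not depend on that assumption.

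No bias or loss of power has been quantified, and the documents give no basis for doing so. The primary endpoint and the WOMAC analyses are unaffected. The change is still worth making: it is nearly free and gives a declared secondary endpoint a baseline-adjusted comparison like the others.

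**What to change.** In SAP 16.2, add an analysis of change from baseline in PGA (0-100) on the ITT set, using the same mixed model as WOMAC. Report the linear trend and the pairwise differences from placebo with 95% CIs. In SAP 19.1, change the treatment-phase entry for PGA to descriptive and analysis. Keep the counts per score as they are.

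If description only is intended, the minimum is an entry in Section 9 with the reason. That cures the undeclared departure but still leaves the endpoint without an estimate.

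The cost is one more run of the Section 11 code with a different response variable. PGA is collected at the same visits as WOMAC, so no new data are needed. The change should be made before the partial database lock. After that, SAP Section 5 would require the analysis to be identified in the trial report as not specified in the SAP.

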16.3 Pharmacokinetic Endpoint Analyses

Pharmacokinetics (PK)

Analyses relating to this endpoint will be conducted by Merck Serono QPD and ECS using the PK Analysis Set.

The data will be reviewed for implausible concentration data. Exclusion of implausible values will be decided by the responsible PK/Pharmacodynamic(s) (PD) representative and/or the Clinical Pharmacology Representative and will be documented in the CTR. If necessary, the subject will be excluded from analysis.

Quality control procedures for the pharmacokinetic analysis will be performed in accordance with the QPD Standard Operating Procedures (SOPs) at Merck Serono.

In case no measurable sprifermin could be detected either in serum or in synovial fluid this will be described in the CTR but no Tables, Listings and Figures (TLFs) will be provided.

Pharmacokinetics based on concentrations measured in the serum

Blood samples for the quantification of sprifermin are collected pre-dose at the baseline visit Week 0/Visit 2, 2 hours after the last dose of each cycle and at the end of the DBPC treatment phase (Visit 22).

Serum levels of sprifermin (pg/mL) will be determined under the responsibility of QPD and will be stored in the PPD

. QPD will produce a separate bio-analytical report. The lower limit of quantification will be 100 pg/mL.

Before DBPC database lock reconciliation of blinded data will be performed. After DBPC database lock final data will be mapped to SDTM and returned to Merck Serono Data Management.

QPD will be responsible for the descriptive statistics on the serum concentrations of sprifermin and TLFs will be provided for the CTR, as applicable.

The following descriptive statistics will be presented for the PK Analysis Set by treatment group and time-point: Number (N) of observations, mean, SD, median, min, max, and coefficient of variation (%CV), if applicable. Individual and mean concentrations will be plotted by treatment group and time-point, if applicable.

Pharmacokinetics based on concentrations measured in the synovial fluid

Synovial fluid for the quantification of sprifermin is collected at visits where IMP is injected. Synovial fluid will be collected as part of the i.a. injection procedure, thus pre-dose synovial fluid samples are collected prior each IMP injection. Synovial fluid levels of sprifermin will be determined under the responsibility of QPD and will be stored in the PPD . QPD will produce a separate bioanalytical report. The lower limit of quantification will be 150 pg/mL.

Before DBPC database lock reconciliation of blinded data will be performed. After DBPC database lock final data will be mapped to SDTM and returned to Merck Serono Data Management. QPD will be responsible for the descriptive statistics on the synovial concentrations of sprifermin and TLFs will be provided for the CTR, as applicable. The following descriptive statistics will be presented for the PK Analysis Set by treatment group and time point: Number (N) of observations, mean, SD, standard error of the mean (SEM), median, min, max, and %CV, if applicable. Individual and mean concentrations will be plotted by treatment group and time-point, if applicable.

Occurrence of antibodies against FGF18 (FGF18ab)

Analyses relating to this endpoint will be conducted by Merck Serono QPD and ECS using the Safety Analysis Set and will be reported in the Safety Section of the CTR.

Blood samples for the determination of the presence of anti-FGF-18 are collected at the baseline visit Week 0/Visit 2, at the first dose of each cycle, 1 week after the last dose of each treatment cycle (at Weeks 3, 29, 55 and 81/Visit 5, 10, 15 and 20) and at the end of the DBPC treatment phase (Week 104/Visit 22).

The presence of anti-FGF-18 antibodies will be determined under the responsibility of QPD and will be stored in the PPD . QPD will produce a separate bioanalytical report.

Before DBPC database lock reconciliation of blinded data will be performed. After DBPC database lock final data will be mapped to SDTM and returned to Merck Serono Data Management. QPD will be responsible for the data analyses and TLFs for the CTR. The data will be summarized by overall frequency and by treatment and time point, if applicable.

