Based on the results described above, this phase II trial is proposed to assess the dose-response-relationship of sprifermin in subjects with knee OA of Kellgren-Lawrence grades 2 and 3. The trial design is presented in Section 5.1; rationales for choices of trial design, subject population, dose regimen, and trial assessments are presented in Section 5.2, and the reasoning behind the choice of planned sample size is presented in Section 8.1.

This clinical trial will be conducted in compliance with the clinical trial protocol, Good Clinical Practice (ICH Topic E6, GCP) and the applicable regulatory requirements.

If the trial is positive, it will provide data on an optimized dose and dosing schedule of sprifermin, i.e., a dose and dosing schedule of the drug that will exert a disease-modifying action (i.e., both modification of structure and improvement of symptoms).

Currently very little is known about how modification of structure is linked to change in symptoms (i.e., perception of pain and function by the subject). This trial will also help to understand how change in cartilage structure correlates with change in symptoms.

To date, a total of 265 subjects have been included in the FIM and the POC trials using i.a. administration. All systemic levels of sprifermin/FGF-18 measured to date have been below the lower limit of quantitation (LLOQ), and no local or systemic safety issues have emerged. No systemic antibodies to sprifermin/FGF-18 have been detected, except in 3 subjects who already tested positive for binding antibodies at baseline. There may be a slightly higher incidence of AIRs in the target knee with dosages of 300 mcg sprifermin; however, the 300 mcg dosage will not be used in this trial. Considering all clinical and non-clinical experience, sprifermin can be regarded as having a favorable safety profile.

The risk-benefit relationship has been carefully considered in the planning of the trial. Based on the pre-clinical and clinical data available to date, the conduct of the trial is considered justifiable using the doses and dosage regimen of the Investigational Medicinal Product (IMP) as specified in this clinical trial protocol.

4 Trial Objectives

The trial's objectives are as follows.

Primary

- To evaluate structural changes in cartilage thickness in the total femorotibial joint of the target knee in terms of imaging by MRI

Secondary

- To evaluate different dose regimens of sprifermin
- To evaluate changes in symptoms of OA

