8.3.3 Safety Endpoints

Safety endpoints are:

- Nature, incidence and severity of local and systemic AEs
- Incidence of acute inflammatory reactions (AIRs), defined as increase of pain by 30 mm on a 100 mm VAS associated with a self-reported synovial fluid effusion (i.e., joint swelling) within 3 days following i.a. injection
- Changes in laboratory safety parameters, vital signs, 12-lead ECG parameters, weight, and physical examinations
- Incidence of surgical interventions in the target knee (including any surgical revision, cartilage removal, or any other type of surgical intervention)
- Occurrence of binding and neutralizing antibodies to sprifermin/FGF-18

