17.3 Clinical Laboratory Evaluation

The following safety laboratory parameters are measured

Hematology

- White blood cell (WBC) count
- Lymphocytes (absolute count, %)
- Monocytes (absolute count, %)

Sprifermin (AS902330) Statistical Analysis Plan (Final) EMR700692 006-v1.0

- Neutrophils (absolute count, %)
- Eosinophils (absolute count, %)
- Basophils (absolute count, %)
- Red blood cells
- Hematocrit
- Hemoglobin
- Platelets

Clinical biochemistry

- Aspartate aminotransferase (AST)
- Alanine aminotransferase (ALT)
- Alkaline phosphatase (ALP)
- Total protein
- Total bilirubin
- Creatine kinase (CK)
- Creatinine
- Calcium
- Phospate
- Sodium
- Potassium
- Magnesium
- Urea (Blood urea nitrogen (BUN))
- Glucose (not fasting)
- Chloride
- Albumin
- High-sensitivity C-reactive protein (hsCRP)
- Erythrocyte sedimentation rate (ESR)

Urinalysis

- Dipstick parameters
- pH
- Specific gravity

Sprifermin (AS902330) Statistical Analysis Plan (Final) EMR700692 006-v1.0

- Protein
- Glucose
- Ketones
- Bilirubin
- Blood
- Urobilinogen
- Leukocytes

Antibodies to sprifermin /FGF-18 (if data available)

- Binding antibodies
- Neutralizing antibodies

Coagulation parameters

- Partial thromboplastin time (PTT)
- International Normalized Ratio (INR)

Pregnancy test: Serum during screening, urine at other visits

Hematology, clinical biochemistry and urinalysis parameters and their corresponding change from baseline variables will be summarized by parameter, treatment and timepoint.

Analysis of antibodies to sprifermin will be provided by Merck Serono QPD and presented by number of observations (n), number of missing values (missing), and the count and percentage of subjects with positive findings of antibodies by treatment and time point, and will be included in the Safety Section of the CTR accordingly as specified in Section 16.3. In case of too low numbers of anti-FGF18 antibodies only a listing will be generated.

Reference ranges from the central laboratory will be used to define Lower limit of normal (LLN) and Upper limit of normal (ULN). For the purposes of laboratory parameter summaries, 'low', 'normal' and 'high' are classified as follows: low < LLN; LLN \le normal \le ULN; high > ULN.

A shift table will be used to summarize for each laboratory parameter the number and percentage of subjects experiencing low, normal, high or missing values at each timepoint according to their baseline classification, by treatment group.

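### The planned antibody summaries do not link later results to Week 0 status, so they mix pre-existing with induced anti-FGF-18 antibodies

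*SAP*

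**What the plan says.** Protocol 8.3.3 names as a safety endpoint: "Occurrence of binding and neutralizing antibodies to sprifermin/FGF-18". Protocol 7.4.3 gives the reason for testing: an exogenous protein could induce antibodies, with possible consequences for safety, PK or efficacy. Only samples positive for binding antibodies go on to the neutralizing assay.

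Under SAP 16.3, samples "are collected at the baseline visit Week 0/Visit 2, at the first dose of each cycle", one week after the last dose of each cycle, and at Week 104. That is nine time points: Weeks 0, 3, 26, 29, 52, 55, 78, 81 and 104.

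The analysis rule stands in two places. SAP 16.3: "The data will be summarized by overall frequency and by treatment and time point, if applicable". SAP 17.3 plans "the count and percentage of subjects with positive findings of antibodies by treatment and time point", and adds: "In case of too low numbers of anti-FGF18 antibodies only a listing will be generated". It gives no threshold for too low.

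On earlier experience, Protocol 3 (Rationale for the Present Trial) says: "To date, a total of 265 subjects have been included in the FIM and the POC trials", and then: "No systemic antibodies to sprifermin/FGF-18 have been detected, except in 3 subjects who already tested positive for binding antibodies at baseline".

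**The concern.** The testing is there to show whether sprifermin induces antibodies. That is a question about change within a subject, from negative before the first injection to positive afterwards. The stated rule counts positives in each arm at each visit and overall, without regard to what the same subject showed at Week 0. A subject positive at Week 0 and unchanged for two years counts in the overall frequency and can count again in all eight later rows, exactly like a subject who converted.

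The exclusion criteria do not remove subjects with pre-existing antibodies, and the earlier trials show that such subjects exist. Elsewhere in safety the SAP does use baseline: treatment-emergent adverse events must start or worsen on or after first dose (17.1), routine laboratory values and ECG have change from baseline (17.3, 17.6), and blood pressure shifts are grouped by baseline category (17.4). The laboratory shift table does not fill the gap, because it classifies values against LLN and ULN and so does not fit a positive/negative result.

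At stake is the immunogenicity statement in the safety section of the trial report. With only a handful of positives, a few pre-existing ones could look like an antibody signal in one arm, or hide a real one.

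**Working it through.** The documents give no rate or sample size for this endpoint. The figure that can be reproduced is the prior denominator: 73 (first-in-man trial) + 192 (proof-of-concept trial) = 265, as stated.

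**1. Prior data under each rule**
- Any positive counts: 3/265 = 1.13%, Clopper-Pearson 95% CI 0.23% to 3.27%.
- Baseline positives removed: 0/(265 − 3) = 0/262. The upper limit of the two-sided 95% interval is 1 − 0.025^(1/262) = 1.40%.

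The same data therefore read as about 1% positive or as no induced antibodies, depending only on the rule.

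**2. Expected baseline positives in this trial**, assuming 3/265 carries over and all randomized subjects are sampled
- All 545 subjects: 545 × 3/265 = 6.2; over the CI, 545 × 0.00234 = 1.3 to 545 × 0.0327 = 17.8.
- Per group of 109: 109 × 3/265 = 1.2 (0.3 to 3.6). The chance of at least one in a given group is 1 − (1 − 3/265)^109 = 71%.

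**3. Share of ever-positive subjects that is pre-existing**

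Let p = 3/265 and let t be the proportion of baseline-negative subjects who convert, averaged over the trial. The share is p / [p + (1 − p)t]. The documents give no t, so a range is shown.

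| Assumed t | Pre-existing share |
|---|---|
| 0 | 100% |
| 0.5% | 70% |
| 1% | 53% |
| 2% | 36% |
| 5% | 19% |
| 10% | 10% |

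For 2%: 0.01132 / (0.01132 + 0.98868 × 0.02) = 0.364.

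**4. Chance imbalance with six baseline positives over five equal arms**
- Placebo has none: 0.8^6 = 26%.
- Some arm has three or more: of 5^6 = 15,625 allocations, 900 + 5,400 + 1,800 = 8,100 leave every arm with at most two (patterns 2-2-2-0-0, 2-2-1-1-0 and 2-1-1-1-1). So 1 − 8,100/15,625 = 48%.

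The placebo arm is thus a weak guide to background positivity at these counts.

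**5. What the by-visit rows can show**

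Suppose one arm has one positive at Week 0 and one at Week 104. This may be one persistent pre-existing positive. It may also be a baseline positive who left the trial plus a different subject who converted. Protocol 8.1 expects 30% discontinuation by two years, so the second reading is plausible, and the table cannot tell the two apart.

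**The case against.** The plan does more than it may seem at first. Week 0 is one of the tabulated time points, so baseline positives per arm will be visible and an imbalance at entry can be read off directly. SAP 11 says data will in general be listed by treatment group, subject and time point, and SAP 17.3 falls back to a listing when antibody numbers are low. With about six positives, a reader could follow each subject by hand. Table shells (SAP 19) and the bioanalytical report (SAP 16.3) are separate documents and may separate baseline status. The endpoint is descriptive, with no test or decision rule.

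All of this stands as mitigation. It does not supply the missing link. The Week 0 row is a marginal count, the overall frequency has no baseline separation at all, the listing-only rule has no threshold, and a listing is not a prespecified definition of conversion. The SAP text does not require the shells to add one.

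Two stronger readings are tempting. A reader might infer that every positive sample is counted. SAP 17.3 counts subjects; only the overall frequency in 16.3 leaves its unit unstated. A reader might also infer from 3 of 3 that all positives in this trial would be pre-existing. That describes earlier trials with one treatment cycle (first-in-man) or two (proof of concept) in their multiple-dose regimens, whereas this trial has four cycles of injections, all of them sprifermin in two arms. The upper limit of 1.40% for 0/262 would still allow about 0.0140 × 545 = 7.6 new positives, more than the 6.2 expected at baseline.

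**Conclusion.** The concern holds in a limited form. As written, SAP 16.3 and 17.3 do not distinguish pre-existing from treatment-emergent antibodies in the overall frequency or in any post-baseline row, although the sample needed to do so is planned for every subject at Week 0. If the prior rate applies, about 6 of 545 subjects (1.3 to 17.8) would enter positive. They would be the majority of ever-positive subjects at conversion rates up to about 1%, a minority above that, and all of them only if nobody converts.

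These figures rest on two assumptions: that 3/265 carries over, although 265 is the number of subjects included and the number tested is not given; and the conversion rates, which are illustrative. The gap in the rule does not depend on either. The consequence is confined to the immunogenicity conclusion. The primary result and the data collection are untouched.

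**What to change.** In SAP 16.3 and 17.3, report by arm and overall:

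- (a) subjects positive at the last sample before the first injection of Cycle 1. Name that injection, because the samples taken at the first dose of later cycles are also pre-dose;
- (b) treatment-emergent positives, as the main immunogenicity summary: negative at that sample and positive at any later one, with baseline-negative subjects who have at least one post-dose sample as the denominator;
- (c) a separate listing of baseline-positive subjects with their later results, including any rise in response if titre is available, so that a boosted response is not lost.

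Do the same for neutralizing antibodies, and state how samples not sent for the neutralizing assay are counted. State that overall frequency counts subjects, and give the threshold below which only a listing is produced.

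The cost is a few sentences in the SAP and an added column and listing in the shells, which SAP 19 allows to be finalized up to unblinding. No further samples are needed.
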